## 9 APPENDICES

### 9.1 COVID-19 Visit Impact

Analyses are based on the COVID-19 Visit Impact CRF.

#### 9.1.1 *COVID-19 Visit Impact CRF Description*

At each visit (scheduled or unscheduled), sites complete the COVID-19 Visit Impact CRF.

Unscheduled visits are identified from visit labels containing “unscheduled”. Otherwise, all other visits are considered scheduled. In listings, the COVID-19 visit type is abbreviated as “U” for unscheduled visits and blank (i.e., missing) otherwise.

COVID-19 visit impact status is based on the response to the lead question “Was this visit impacted by COVID-19 related issues? (yes or no)”. In listings, the COVID-19 visit impact status is abbreviated as “&” for yes and “#” for no.

If the response to the lead question is “yes”, then responses to the following questions are provided:

- **COVID-19 visit impact type:** What was the impact? (indicate one)
  - (1) Missed visit – no assessments done [abbreviated COVID-19 impact type = “M” in listings]
    - Date visit planned to occur [used to derive the COVID-19 visit date]
  - (2) In-person visit at site (check all that apply) [abbreviated COVID-19 impact type = “I” in listings]
    - Not all assessments completed [abbreviated as “N” in listings] \*
    - Scheduled visit occurring earlier or delayed relative to protocol specified schedule [abbreviated as “S” in listings] \*
  - (3) Remote visit (indicate one) [abbreviated as “R” in listings]
    - Virtual visit (video/telemedicine) [abbreviated as “V” in listings] \*
    - Telephone contact [abbreviated as “T” in listings] \*
- Subcategories marked with “\*” are visit impact characteristics.
- **COVID-19 visit impact relationship:** How was the impact related to COVID-19? (check all that apply)
  - Subject diagnosed with COVID-19 or quarantined due to COVID-19 [abbreviated as “1” in listings]
  - Site closed or access restricted due to COVID-19 [abbreviated as “2” in listings]
  - Site open but subject unwilling or unable to come to the site due to COVID-19 [abbreviated as “3” in listings]
  - Other [abbreviated as “4” in listings], with specify text
- **COVID-19 premature study termination:** If the subject is terminating the study prematurely, was the termination related to COVID-19? (yes; no; not applicable) [abbreviated as “X” for yes, “Z” for no, and blank otherwise in listings].

### **9.1.2      ***COVID-19 Impact*****

A subject is impacted by COVID-19 if there is a “yes” response to the lead question at  $\geq 1$  visit.

### **9.1.3      ***COVID-19 Visit Impact*****

A visit is impacted by COVID-19 if there is a “yes” response to the lead question at that visit (see Section 9.1.1).

A visit is not impacted by COVID-19 if there is a “no” response to the lead question at that visit.

### **9.1.4 COVID-19 Premature Study Termination**

A subject terminated the study prematurely due to COVID-19 if all of the following criteria are met: “yes” response to the COVID-19 premature study termination question at  $\geq 1$  visit (see Section 9.1.1); did not complete the study (see Section 6.2.3). Reasons for premature termination are based on the reasons for early discontinuation (i.e., not completing the study).

### **9.1.5 COVID-19 Visit Impact Code**

#### **9.1.5.1 COVID-19 Visit Impact Code Derivation**

At each visit, the COVID-19 visit impact code is derived as follows:

- If the visit is impacted by COVID-19, then the value is the concatenation of the COVID-19 abbreviations described in Section 9.1.1 in the following order:
  - 1) Visit impact status (i.e., lead question response): “&”
  - 2) Visit type: “U” if unscheduled
  - 3) Visit impact type: “M”, “I”, or “R”
  - 4) Visit impact characteristics: “N”, “S”, “T”, or “V”. Both “N” and “S” may be selected for in-person visits.
  - 5) Visit impact relationship: 1, 2, 3, or 4. Multiple responses may be selected.
  - 6) Premature study termination: “X” or “Z”.

Examples:

- “&UINS24X” if visit type is unscheduled, visit impact type is in-person visit, visit impact characteristics are “Not all assessments completed” and “Scheduled visit occurring earlier or delayed relative to protocol specified schedule”, visit impact relationships are “Site closed or access restricted due to COVID-19” and “Other”, and premature study termination is yes.
- “&RT1” if visit type is scheduled, visit impact type is remote visit, visit impact characteristic is “Telephone contact”, visit impact relationship is “Subject diagnosed with COVID-19 or quarantined due to COVID-19”, and premature study termination is not applicable.
- If the visit is not impacted by COVID-19, then the value is the concatenation of the visit impact status “#” and the visit type (“U” if unscheduled).
- Otherwise, the value is blank (i.e., missing).

#### **9.1.5.2 COVID-19 Visit Impact Code in Listings**

Select by-subject listings of measurements over time display all COVID-19 visit impact codes for visits impacted by COVID-19 as additional data records (see Section 9.1.3). Refer to the Mock TLF CSR document for more details.

COVID-19 measurements are slotted into analysis periods and analysis visit windows according to the COVID-19 visit date (see Sections 7.1 through 7.3).

In the listing of COVID-19 impact codes by visit, footnotes describe the abbreviations in the COVID-19 visit impact code, e.g., “COVID-19 visit impact code: & = Impacted; # = Not impacted; I = In-person visit at site; M = Missed visit; N = Not all assessments done; R = Remote visit; S = Scheduled visit early or late; T = Telephone; U = Unscheduled; V = Virtual; X = Premature termination due to COVID-19; Z = Premature termination not due to COVID-19; 1 = Subject dx or quar.; 2 = Site closed or restricted access; 3 = Site open but subject unwilling/unable to come to site; 4 = Other”.

## 9.2 Relevant Protocol Deviations

Relevant eligibility protocol deviations include the following categories:

- LTT participated or treated with study drug more than once and assigned > 1 subject identifier. These subjects are identified from the protocol deviation CTMS file.
- < 2 migraines attacks treated with migraine standard of care medication during the Observation Phase based on the eDiary evening report. Defined as a total of 0 or 1 day in the OP analysis period in which there were “yes” responses to the 2 questions about having a migraine headache and taking any medication other than study medication to treat the migraine headache in the eDiary evening report on the same day.
- Cardiovascular disease risk factor, defined as any of the following subcategories:
  - Ischemic coronary artery disease
  - Other significant underlying cardiovascular disease
  - Coronary artery vasospasm including Prinzmetal’s angina
  - Wolff-Parkinson-White syndrome or arrhythmias associated with other cardiac accessory conduction pathway disorders
  - Other arrhythmias
  - History of stroke or transient ischemic attack
  - Peripheral vascular disease
  - Ischemic bowel disease
  - Uncontrolled hypertension

These are identified from “yes” responses to having risk factors listed above on the Cardiac and Other Risk Factors CRF. Only subcategories with “yes” responses are presented.

- Medical history, defined as any of the following subcategories:
  - Basilar migraine or hemiplegic migraine
  - Active chronic pain syndrome or other pain syndromes other than migraine
  - Dementia or significant neurological disorder other than migraine

- Major depressive disorder with atypical antipsychotics taken during pre-LTT, schizophrenia, bipolar disorder, or borderline personality disorder. PTs must contain any of the following: major depress; schizophrenia; bipolar disorder; borderline personality disorder. Refer to the Zavegeptan Core SAP for atypical antipsychotics.
- Gilbert's syndrome or any other active hepatic or biliary disorder.

For each subcategory, PTs are displayed alphabetically as additional subcategories. Unless specified otherwise, PTs are identified by the Biohaven medical lead or designee from reviewing a list of unique medical history SOC and PTs.

- Finding out of range, defined any as any of the following subcategories:
  - Females with a positive pregnancy test on or after informed consent (see Section 6.4.2)
  - Estimated glomerular filtration rate (eGFR) according to the re-expressed abbreviated (4-variable) Modification of Diet in Renal Disease (MDRD) Study equation  $\leq 40$  mL/min/1.73m^2 during pre-LTT \*
  - BMI  $\geq 33$  kg/m^2 during pre-LTT \*
  - S-STS total score  $> 0$  during pre-LTT.

For the subcategories marked with “\*”, all non-missing values during the pre-LTT analysis period must meet the deviation criteria in order to be considered a deviation.

Relevant subject management protocol deviations include the following categories:

- Study drug dosing error, defined as any of the following subcategories:
  - Study drug taken but not participated in the LTT phase
  - Administered  $> 1$  spray on any 1 day (see Section 6.2.6.1)
  - Administered  $> 8$  sprays per month in any 1 month (see Section 6.2.6.1).
- eDiary site or subject usage compliance  $< 80\%$  from LTT start to end (see Section 6.2.6.2)
- Prohibited non-study medications, defined as any of the following subcategories:
  - Atypical antipsychotics, divalproex, valproic acid, or valproate taken on or after informed consent #
  - Barbiturate taken up to 14 days before LTT start or afterward #
  - Butterbur root or extract taken up to 14 days before LTT start or afterward
  - Ergotamine, lasmitidan, or triptan taken up to 2 days before LTT start or afterward #
  - Gepant taken on or after informed consent #
  - Lamotrigine taken on or after informed consent
  - Medication administered nasally (1) anytime during pre-LTT, or (2) for  $\geq 10$  days (not necessarily consecutive) per month on or after LTT start #. Route must be nasal. For criterion (2), the following applies:

- Analyses are similar to study drug exposure in which results are not prorated to 28 days (see Section 6.2.6.1). However, analyses are based on all months (4-week intervals) during the LTT and follow-up analysis periods combined. Meeting the criteria in  $\geq 1$  month (4-week interval) is considered a deviation. Days in which medication is taken are determined using imputed medication start and stop dates across all records with nasal route. If the frequency is at least QD (i.e., QD, BID, TID, QID, QM, or QHS), then all days in the specified time period that are between the imputed start date and imputed stop date inclusive count. If the frequency is PRN, then all days in the specified time period that are equal to the imputed start date or imputed stop date count. If the frequency is other, then all days in the specified time period that are equal to the imputed medication start date count.
- Muscle relaxant (excluding baclofen) taken on or after LTT start #
- Narcotic taken up to 2 days before LTT start or afterward #
- Select strong cytochrome P450 3A4 (CYP3A4) inducers taken up to 14 days before study drug #. These are non-study medications with (1) study drug date – 14  $\leq$  imputed start or imputed stop date  $\leq$  study drug date, or (2) imputed start date  $\leq$  study drug date – 14  $<$  study drug date  $\leq$  imputed stop date. All study drug dates are considered.
- Select strong CYP3A4 inhibitors taken up to 14 days before study drug #.

For the subcategories marked with “#”, preferred names are displayed alphabetically as additional subcategories. See Section 6.2.5.4 for the definition of medication taken during pre-LTT. See Section 6.2.6.3 for the definition of medication taken on or after LTT start. Medications taken up to  $X$  days before a reference date or afterward are defined as those with imputed medication start date or imputed stop date  $\geq$  reference date –  $X$ . Refer to the Zavegeptan Core SAP for additional details about prohibited non-study medications.

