4.3.2 Pre-Baseline Visit

Screened subjects will be assessed for eligibility based on data collected at the screening visit, during the observation phase, and at the pre-baseline visit. The pre-baseline visit should be completed within 5 days of the baseline visit. This visit must be conducted in person.

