4.3.3 Baseline Visit

The baseline visit should occur within 28 days (+/- 2 days) of the screening visit. If the pre-baseline laboratory test results are determined to be unacceptable per protocol, the subject is considered a screen failure and must return to the study site to return the provisioned device (if applicable). Eligible subjects will be dispensed study drug at this visit. This visit must be conducted in person.

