 - ii) Detectable levels of marijuana in the drug screen are not exclusionary, if in the Investigator's documented opinion the subject does not meet DSM-V criteria¹³ for substance use disorder, and the positive test does not signal a clinical condition that would impact the safety of the subject or interpretation of the study results.
- r) Hematologic or solid malignancy diagnosis within 5 years prior to the screening visit. Subjects with a history of localized basal cell or squamous cell skin cancer are eligible for the study if they are cancer-free prior to the screening visit in this study.
- s) Body mass index $\geq 33 \text{ kg/m}^2$
- t) Patient has a history or diagnosis of Gilbert's Syndrome or any other active hepatic or biliary disorder.
- 3) Allergies and Adverse Drug Reactions

a) History of drug or other allergy which, in the opinion of the Investigator, makes the subject unsuitable for participation in the study.

4) Sex and Reproductive Status

- a) Females of child-bearing potential who are unwilling or unable to use acceptable contraceptive methods (see Section 5.6) to avoid pregnancy for the entire study period and for 90 days after the last dose of study drug.
- b) Women who are pregnant, lactating or breastfeeding.
- c) Women with a positive pregnancy test
- 5) ECG and Laboratory Test Findings
 - a) Estimated glomerular filtration rate (eGFR) according to the re-expressed abbreviated (four-variable) Modification of Diet in Renal Disease (MDRD) Study equation ≤ 40 ml/min/1.73m².
 - b) Corrected QT interval > 470 msec (QTc by method of Frederica), at screening.
 - c) Left Bundle Branch block.
 - d) Right Bundle Branch Block with a QRS duration ≥ 150 msec.
 - e) Intraventricular Conduction Defect with a QRS duration ≥ 150 msec.
 - f) Serum bilirubin (total, direct, or indirect) > 1 x ULN at pre-baseline visit (Only abnormal values of between 1-1.5x ULN at the screening visit may be repeated once for eligibility during the observation phase. Abnormal bilirubin results obtained at the pre-baseline visit may not be repeated.)
 - g) Neutrophil count ≤ 1000/µL (or equivalent) at screening or pre-baseline visit.
 - h) AST (SGOT) or ALT (SGPT) > 1 x ULN at pre-baseline visit. (Only abnormal values of between 1-1.5x ULN at the screening visit may be repeated once for eligibility during the observation phase. Abnormal AST or ALT results obtained at the pre-baseline visit may not be repeated.)
 - i) HbA1c > 6.5% at screening visit.

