## 7.2 Analysis Periods

Analysis periods are defined as follows:

- OP: measurement date/time on or after the OP start date/time through the OP end date/time. This period is used to assess the number of migraine days per month during the OP.
- Pre-treatment: measurement date/time on or before the study drug start date/time. This period is used to derive baseline values, and to assess safety and outcomes research endpoints. Note that all measurements are pre-treatment for subjects in the enrolled analysis set with missing study drug start date.
- Pre-LTT: measurement date/time on or before the LTT start date/time. This period is used to derive analysis visit windows for slotting observations. Note that all measurements are pre-LTT for subjects in the enrolled analysis set with missing LTT start date.
- LTT: measurement date/time after the LTT start date/time through the LTT last date. This period is used to derive analysis visit windows for slotting observations, and to assess exposure and migraine days during LTT. Note that AEs with imputed start date equal to the

LTT start date are part of this period (refer to the Zavegeptan Core SAP for AE start date imputation).

- Follow-up: measurement date after the LTT last date. This period is used to slot observations.
- On-treatment safety: measurement date/time after the study drug start date/time through the study drug last date + 7 days. This period is used to assess safety endpoints on treatment.  
Note that AEs with imputed start date equal to the study drug start date are part of this period.
- Follow-up safety: measurement date after the study drug last date + 7 days. This period is used to assess safety endpoints during follow-up.

See Section 7.1 for derived dates for determining analysis periods. If measurement time is missing, not collected, or not applicable for a parameter, then the measurement date is compared to the derived date.

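### SAP 9.2 counts an eGFR or BMI eligibility deviation only if every pre-LTT value fails, so a treated subject with a passing screening value and a failing pre-baseline value is not counted

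*SAP*

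**What the plan says.** SAP 9.2 defines the relevant eligibility deviations. Under findings out of range, the eGFR and BMI items carry an asterisk, and for those items "all non-missing values during the pre-LTT analysis period must meet the deviation criteria in order to be considered a deviation". SAP 7.2 defines the window: "Pre-LTT: measurement date/time on or before the LTT start date/time". It therefore takes in the screening value, the pre-baseline value and any unscheduled value between them.

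SAP 6.2.4.1 sends these deviations to a table for the full analysis set and a by-subject listing for the enrolled set. Unless otherwise specified, categories with a zero count are still printed.

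Protocol 5.3, exclusion 5a, excludes subjects by eGFR ("four-variable) Modification of Diet in Renal Disease (MDRD) Study equation ≤ 40"). Exclusion 2s excludes a BMI of 33 kg/m² or more. Neither names a visit or provides for a repeat.

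Protocol 4.3.2 states the evidence for eligibility: "Screened subjects will be assessed for eligibility based on data collected at the screening visit, during the observation phase, and at the pre-baseline visit". Protocol 4.3.3 states the consequence of a failing laboratory result: "If the pre-baseline laboratory test results are determined to be unacceptable per protocol, the subject is considered a screen failure".

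**The concern.** The counting rule works as a best-value rule: one passing value anywhere before LTT start cancels the deviation. The protocol gives no such allowance for eGFR or BMI. Where it wanted a repeat to count for eligibility it said so, and only for bilirubin and AST/ALT between 1 and 1.5 times ULN at screening. It also barred repeats of those tests at pre-baseline.

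The pattern the rule drops is one where the most recent scheduled value before dosing was exclusionary. Because zero rows are printed, a zero for eGFR or BMI could be read as showing that no treated subject breached the criterion, when it shows only that none failed on every value. Each additional measurement can only lower the count, never raise it.

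**Working it through.** The plan states no figure to reproduce. The check is of what the rule counts.

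**Inputs**
- Chemistry: screening and pre-baseline (SAP 6.4.2, Protocol Table 1). eGFR is part of the clinical safety laboratory panel (Protocol 6.3.4.1).
- BMI: weight at screening and pre-baseline (Protocol Table 1), height at screening only (SAP 6.4.3).
- Thresholds: eGFR at or below 40, BMI at or above 33 (Protocol 5.3).

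**Patterns for two scheduled values under three rules**

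| Screening | Pre-baseline | SAP 9.2: all fail | Last value fails | Any value fails |
|---|---|---|---|---|
| pass | pass | no | no | no |
| pass | fail | **not counted** | counted | counted |
| fail | pass | not counted | not counted | counted |
| fail | fail | counted | counted | counted |
| fail | missing | counted | counted | counted |
| missing | fail | counted | counted | counted |

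The second row is the problem. For eGFR, Protocol 4.3.3 makes that subject a screen failure whatever the screening value was. If the subject is treated anyway, SAP 9.2 records no eGFR deviation. For example, an assumed eGFR of 45 at screening and 37 at pre-baseline is not counted.

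The third row is also uncounted. Since exclusion 5a has no repeat provision, that pattern should at least be visible.

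**BMI example (assumed height and weights).** With height 1.65 m, height squared is 2.7225. Screening weight 89.5 kg gives 89.5 / 2.7225 = 32.87. Pre-baseline weight 90.2 kg gives 90.2 / 2.7225 = 33.13. The later value meets exclusion 2s, but SAP 9.2 counts nothing. If no later weight precedes the first dose, SAP 6.2.5 takes 33.13 as baseline BMI, so the baseline data and the deviation table disagree for that subject.

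**Illustration of sensitivity.** Let p be the probability that one measurement meets the criterion, with two independent normal measurements. The last-value rule counts p and the SAP rule counts p². The share of last-value failures missed is (p − p²)/p = 1 − p. The within-person variability below is assumed; the documents give none.

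| Assumed true value | Assumed variability | p | Share missed |
|---|---|---|---|
| eGFR 40 | any | 0.50 | 0.50 |
| eGFR 42 | CV 5% to 10% | 0.17 to 0.32 | 0.83 to 0.68 |
| eGFR 38 | CV 5% to 10% | 0.85 to 0.70 | 0.15 to 0.30 |
| BMI 33.0 | any | 0.50 | 0.50 |
| BMI 33.2 | SD 0.2 to 0.35 | 0.84 to 0.72 | 0.16 to 0.28 |

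For example, eGFR 42 with CV 5% has SD 2.1, so p = Φ((40 − 42)/2.1) = Φ(−0.95) = 0.17.

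These shares do not describe the treated population. The model lets everyone through to treatment, whereas a failing screening value should already have stopped many subjects and a failing pre-baseline laboratory value should stop the rest. They show only that a borderline subject can easily pass once and fail once.

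**The case against.** The strongest reply is that the SAP 9.2 table is a selected set of programmed checks and not the only record of eligibility. It has no row for AST/ALT, QTc, neutrophils or HbA1c, although all are exclusions. The same subject may appear in the inclusion/exclusion listing (SAP 6.2.3) or in the CTMS listing of major deviations (SAP 6.2.4.2). The raw values are in the laboratory and physical-measurement listings for the enrolled set (SAP 6.4.2 and 6.4.3). None of these uses the asterisk rule. This stands, and it limits the harm. It does not remove it: the first two depend on a site recording the breach, the CTMS listing also on its being graded major, and the value listings do not mark deviations.

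Three stronger readings are tempting but not supported:

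- *That these subjects are reported as eligible.* No output labels anyone eligible on the strength of this rule. They are only missing from one table and listing.
- *That SAP 9.2 contradicts itself because the S-STS item has no asterisk.* Exclusion 6e names the screening or pre-baseline visit for S-STS, so counting any positive score follows the protocol. Exclusions 5a and 2s name no visit.
- *That the rule allows dosing at an eGFR where Protocol 6.6 requires discontinuation.* The threshold is the same, but a tabulation rule neither permits nor prevents dosing.

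The BMI half also deserves a discount. Protocol 4.3.3 speaks of laboratory results, and BMI is not one. What remains is that Protocol 4.3.2 draws on data from both visits and exclusion 2s is unqualified.

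Finally, a last-value rule would still leave fail-then-pass uncounted, although the protocol gives no repeat allowance. That is fair, and is why the fix adds a flag.

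**Conclusion.** The point holds as a small correction to deviation reporting. For eGFR, SAP 9.2 contradicts Protocol 4.3.3 and exclusion 5a: it does not count a treated subject whose pre-baseline result failed after a passing screening result. For BMI the rule sits poorly with Protocol 4.3.2 and exclusion 2s, but no passage contradicts it as directly.

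The consequence is an under-count of eligibility deviations in the SAP 9.2 table and listing. Its size cannot be computed, because the documents give neither the distribution of eGFR or BMI nor their within-person variability. The percentages above are illustrations under assumed values. Analysis sets are not defined by deviations (SAP 4.1), so denominators and the primary safety frequencies are unaffected. That the rule misses the pass-then-fail pattern follows from the text alone and needs no assumption.

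**What to change.** In SAP 9.2, replace the asterisk rule with: a deviation is counted if the last non-missing value on or before LTT start meets the criterion. In the relevant-deviation listing, also flag any subject with any pre-LTT value meeting the criterion, so that fail-then-pass cases are visible.

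This follows the same last-value principle as the SAP 6.2.5 baseline but is not identical to it. For the safety set, baseline runs to the first dose, and with as-needed dosing that can fall after LTT start. LTT start is the better anchor here because the eligibility decision is made at the baseline visit.

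The cost is one SAP sentence and minor programming. The reported deviation count may rise slightly.
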